Appendix E LA Classification of Esophagitis Grading System

LA Classification of Esophagitis Grading System	
Grade	Definition
O	No mucosal breaks
A	One (or more) mucosal break no longer than 5 mm that does not extend between the tops of 2 mucosal folds.
B	One (or more) mucosal break more than 5 mm long, that does not extend between the tops of 2 mucosal folds.
C	One (or more) mucosal break that is continuous between the tops of 2 or more mucosal folds, but which involves less than 75% of the circumference.
D	One (or more) mucosal break, which involves at least 75 % of the esophageal circumference.

Appendix F GERD Symptoms Investigator Assessments

Definitions of GERD Symptoms Assessed by Investigator

Symptom	Definition
Heartburn	A burning feeling in the mid-epigastric area and/or chest area.
Acid Regurgitation	Flow of sour or bitter fluid into the mouth.
Dysphagia	Difficulty in swallowing.
Belching	The voiding of gas from the stomach through the mouth, which may have been associated with acid regurgitation.
Epigastric Pain	Central upper abdominal pain.

Definitions of GERD Symptoms Severity by Investigator

Severity	Definition
None	No symptoms.
Mild	Symptom did not last long and was easily tolerated.
Moderate	Symptom caused discomfort and/or interrupted usual activities (including sleep).
Severe	Symptom caused great interference with usual activities and may have been incapacitating (including sleep).
Very Severe	Symptom caused intense and constant discomfort and/or marked interference with usual activities (including sleep).

Appendix G Definition of Heartburn Severity (Daytime/Nighttime)

Definitions of Daytime Heartburn Severity (Daytime=Awake Time)

None	No heartburn.
Mild	Occasional heartburn, can be ignored, does not influence daily routine.
Moderate	Heartburn cannot be ignored and/or occasionally influences daily routine.
Severe	Heartburn present most of day and/or regularly influences daily routine.
Very Severe	Constant heartburn and/or markedly influences daily routine.

Definitions of Nighttime Heartburn Severity (Nighttime=Sleep Time)

None	No heartburn.
Mild	Occasional heartburn, can be ignored, does not influence sleep.
Moderate	Heartburn cannot be ignored and/or occasionally influences sleep.
Severe	Heartburn present most of night and/or regularly influences sleep.
Very Severe	Constant heartburn and/or markedly influences sleep.

Appendix H Diary

The following diary questions will be asked in the morning:

1. Did you have heartburn last night? Yes No

If yes, what was the maximum severity? Choose 1.

- Mild
- Moderate
- Severe
- Very Severe

2. Did you take any rescue medication last night? (such as Talcid chewable tablets, Gaviscon tablets and/or other antacids) Yes No

The following diary questions will be asked in the evening:

1. Did you have heartburn today? Yes No

If yes, what was the maximum severity? Choose 1.

- Mild
- Moderate
- Severe
- Very Severe

2. Did you take any rescue medication today? (such as Talcid chewable tablets, Gaviscon tablets and/or other antacids) Yes No

Appendix I Detailed Description of Amendments to Text

This appendix describes content changes in reference to Protocol Incorporating Amendment No. 03 dated 20 February 2017.

Change 1: Update contract research organization (CRO) contact information.

The change occurs in Section 1.1 [Contacts](#):

Description of change: Changed the contact for SAE, pregnancy, and special interest adverse event reporting from [name] to [name]. The methods of contact were updated accordingly.

Rationale for Change: The contact was updated to reflect a change in responsibilities at the CRO.

Change 2: Change the appropriate contact for confirming available brands of rescue medication.

The change occurs in Section 8.1.1.2 [Rescue Medication](#):

Initial wording: If the listed rescue medications are not available, the subject should contact the contract research organization (CRO) or Takeda Medical Advisor for confirmation of available brand.

Amended or new wording: If the listed rescue medications are not available, the subject should contact the ~~contract research organization (CRO) or Takeda Medical Advisor~~ **subject's responsible investigator** for confirmation of available brand. During the rescue medication administration, the following should be noted:

Rationale for Change: The subject does not need to contact the CRO or Takeda Medical Advisor, but can discuss available rescue medications with the investigator directly.

Change 3: Gastrin levels will be blinded to both investigators and medical monitors during the study period.

The change occurs in Section 9.1.10 Procedures for Clinical Laboratory Samples, Table 9.a, footnote b:

Initial wording: (b) Gastrin levels to be measured under fasting conditions. Gastrin levels above the upper limit of normal will be evaluated by the medical monitor and principal investigator on a case-by-case basis.

Amended or new wording: (b) Gastrin levels to be measured under fasting conditions. ~~Gastrin levels above the upper limit of normal will be evaluated by the medical monitor and principal investigator on a case-by-case basis.~~ **Gastrin levels will be blinded to both investigators and the medical monitor during the study period.**

This change also appears in a later paragraph within the text of Section 9.1.10 Procedures for Clinical Laboratory Samples.

Rationale for Change: Because PPI treatments will be associated with increases in gastrin levels, reviewing these data during the study may reveal the subject's treatment assignment.

Change 4: Clarify acceptable windows for screening labs and endoscopy.

The primary change occurs in Section 9.3.1 Screening.

Initial wording: The screening clinical laboratory tests, hepatitis panel, and endoscopy must be performed within 7 days prior to randomization.

Amended or new wording: The screening clinical laboratory tests, hepatitis panel, and endoscopy must be performed within ~~7~~ **14** days prior to randomization.

Rationale for Change: The window for screening laboratory tests (including hepatitis panel) and endoscopy was extended to 14 days prior to randomization in order to allow greater flexibility for scheduling procedures for subjects who may be eligible for study entry, but without compromising their safety.

The following sections also contain this change:

- Section 6.1 Study Design.
 - Section 9.1.10 Procedures for Clinical Laboratory Samples.
 - Section 9.1.16 Endoscopy.
 - Section 9.3.2 Study Randomization.
 - Appendix A Schedule of Study Procedures.
-

Change 5: Update one of the definitions of an SAE.

The change occurs in Section 10.1.4 SAEs:

Initial wording: 5. Leads to a CONGENITAL ANOMALY/BIRTH DEFECT.

Amended or new wording: 5. ~~Leads to~~ **Is** a CONGENITAL ANOMALY/BIRTH DEFECT.

Rationale for Change: Updated to be the correct definition.

Amendment 3 to A Phase 3 Study to Evaluate the Efficacy and Safety of Dexlansoprazole (60 mg QD) and an Active Comparator, Lansoprazole (30 mg QD) on Healing of Erosive Esophagitis, and Maintenance of Healing in Subjects With Healed Erosive Esophagitis With Dexlansoprazole (30mg QD)

ELECTRONIC SIGNATURES

Signed by	Meaning of Signature	Server Date (dd-MMM-yyyy HH:mm 'UTC')
PPD 	Biostatistics Approval	22-Feb-2017 16:31 UTC
	Clinical Science Approval	22-Feb-2017 17:50 UTC
	Clinical Science Approval	23-Feb-2017 00:59 UTC

3.0 LIST OF ABBREVIATIONS

AE	adverse event
BMI	body mass index
CMH	Cochran-Mantel-Haenszel
EKG	electrocardiogram
EE	erosive esophagitis
FAS-H	Full Analysis Set – Healing Period
FAS-M	Full Analysis Set – Maintenance Period
GERD	gastroesophageal reflux disease
HLT	high level term
MedDRA	Medical Dictionary for Regulatory Activities
MAV	markedly abnormal values
PT	preferred term
QD	once daily
SI	System International
SOC	system organ class
TEAE	treatment-emergent adverse event
TRAE	treatment-related adverse event
WHODrug	World Health Organization Drug Dictionary

4.0 OBJECTIVES

4.1 Primary Objectives

The primary objective is to compare the efficacy of dexlansoprazole capsules (60 mg QD) and lansoprazole capsules (30 mg QD) in healing erosive esophagitis (EE) over 8 weeks of treatment in Chinese subjects with endoscopic evidence of EE; the primary comparison will be to determine whether dexlansoprazole is noninferior to lansoprazole.

4.2 Secondary Objectives

The secondary objective is to compare the efficacy of dexlansoprazole capsules (30 mg QD) and placebo in the maintenance of healing in Chinese subjects with healed EE; the primary comparison will be to determine whether dexlansoprazole is superior to placebo.

4.3 Study Design

This is a phase 3, randomized, double-blind, multicenter, active-controlled, 2-arm study with an initial 8-week healing period with noninferiority design, followed by a randomized, placebo-controlled 6-month maintenance period. The study is designed to evaluate healing, maintenance of healed EE and the effect of therapy on relieving gastroesophageal reflux disease (GERD) related symptoms. Approximately 450 subjects will be enrolled at an estimated 25 sites across China. Further details can be found in the study protocol (Protocol Amendment 3, 20 February 2017).

The study consists of 3 periods; a Screening Period (maximum 21 days), a Healing Period, which will last 8 weeks, and a Maintenance Period of up to 6 months. After signing an informed consent form subjects will undergo a screening evaluation within 21 days prior to the first dose of study drug (Study Day 1). Subjects will be instructed that lifestyle or behavior modifications designed to treat their symptoms of GERD should not be altered throughout the study. Subjects will be given a diary on the first day of the Screening Period. Throughout the Screening Period, subjects will record the presence and maximum severity of daytime and nighttime heartburn symptoms each day in their diary.

During the Screening Period, subjects will undergo various procedures to determine eligibility for the Healing Period. Screening evaluations will include the following: demographics, medical and social history, physical examination including vital signs, height and weight, electrocardiogram (ECG), endoscopy, clinical laboratory evaluations including tests for serum and urine pregnancy (all women of childbearing potential) and hepatitis panel, and concomitant medication assessment. The screening clinical laboratory tests, hepatitis panel, and endoscopy must be performed within 14 days prior to randomization. Endoscopy data will be collected to identify subjects with EE, and only those subjects with endoscopically-confirmed EE Grades A-D as defined by the LA Classification Grading System, will be eligible for this study. Endoscopic pictures will be taken by the study site and kept in the site's source document files according to the site's practice.

Subjects who satisfy the screening evaluation and selection criteria, and have EE confirmed by endoscopy, may be entered into the study. Subjects having an esophageal stricture will be excluded from the study. The endoscope must pass freely into the stomach during the endoscopy.

All subjects will return to the investigative site on Day -1 which will be deemed as the Baseline. Subjects who have completed all of the Screening procedures and met all eligibility requirements and none of the exclusion criteria will have routine fasting laboratory evaluations, including fasting serum gastrin, a urine pregnancy test (all women of childbearing potential), physical examination, and vital signs measurements to assure continued eligibility. Subjects will be dispensed study drug on Study Day -1 according to an interactive web response system and will begin taking study drug on the following day (Study Day 1). In addition, subjects will be assessed for GERD symptoms such as heartburn, acid regurgitation, dysphagia, belching, and epigastric pain by the investigator.

- Subjects will be assigned in a 1:1 ratio to one of the following 2 treatment groups during the 8-week Healing Period; the randomization will be stratified by baseline endoscopic findings (grades A/B or C/D).
 - Group I: dexlansoprazole capsules (60 mg QD).
 - Group II: lansoprazole capsules (30 mg QD).

During the 8-week Healing Period, study drug will be self-administered orally QD before breakfast in the morning. Subjects will document the presence and maximum severity of daytime and nighttime heartburn symptoms using a diary. Subjects will also record the use of rescue medication. Subject visits will be conducted at Weeks 4 and 8 of the Healing Period to collect and/or dispense study drug, assess GERD symptoms, review concomitant medication use, and assess adverse events (AEs).

At the Week 4 Visit, the subject will undergo a physical examination including vital signs, laboratory evaluations, and urine pregnancy test (all women of childbearing potential).

At the Week 8 Visit, all subjects will undergo a physical examination including vital signs, laboratory evaluations, fasting serum gastrin, serum and urine pregnancy test (all women of childbearing potential), ECG and an endoscopy. In addition, study drug will be collected, a review of concomitant medication use will be performed, and an assessment of AEs will be conducted. If the subject's EE has healed completely as determined by endoscopy, the subject will have completed the Healing Period of the study, and will continue in the Maintenance Period. If the subject's EE has not completely healed after 8 weeks of treatment, all Final Visit procedures will be performed and the subject will not be eligible to continue into the Maintenance Period.

For subjects who prematurely discontinue during the Healing Period, efforts should be made to perform all procedures scheduled for the Week 8 / Early Termination Visit no later than 5 days after the last dose of study drug.

At the start of the 6-Month Maintenance Period, subjects with healed EE will be randomized in a 1:1 ratio to one of the following 2 groups; the randomization will be stratified by baseline endoscopic findings (grades A/B or C/D).

- Group I: dexlansoprazole capsules (30 mg QD)
- Group II: placebo (QD)

During the 6-month Maintenance Period, study drug will be self-administered orally, QD in the morning before breakfast. Subjects will continue to document the presence and maximum severity of daytime and nighttime heartburn symptoms using a diary. Subjects will also record the use of rescue medication. Subject visits will be conducted at Months 1, 3 and 6, of the Maintenance Period to collect and/or dispense study drug, assess GERD symptoms, review concomitant medication use, and assess AEs. Endoscopies will be performed at Months 1 and 6/Final Visit to evaluate maintenance of healed EE. Subjects with endoscopic evidence of relapsed EE will be discontinued from the study.

At the Month 1 Visit, the subject will undergo a physical examination including vital signs, laboratory evaluations, endoscopy, and urine pregnancy test (all women of childbearing potential).

[figure not shown]
At the Month 3 Visit, the subject will undergo a physical examination including vital signs, laboratory evaluations and urine pregnancy test (all women of childbearing potential). An optional endoscopy may be performed based on investigator's discretion if the subject presents with GERD symptoms at any time point during the Maintenance Period.

At the Month 6 Visit, all subjects will undergo a physical examination including vital signs, laboratory evaluations, fasting serum gastrin, serum and urine pregnancy test (all women of childbearing potential), endoscopy, and ECG. In addition, study drug will be collected, a review of concomitant medication use will be performed, and an assessment of AEs will be conducted.

For subjects who prematurely discontinue during the Maintenance Period, efforts should be made to perform all procedures (including endoscopy) scheduled for the Month 6 / Early Termination Visit no later than 5 days after the last dose of study drug.

A schematic of the study design is included as [Figure 4.a](#).

Figure 4.a Schematic of Study Design

5.0 ANALYSIS ENDPOINTS

5.1 Primary Endpoints

The primary endpoint is the percentage of subjects who have complete healing of EE over 8 weeks as assessed by endoscopy.

5.2 Secondary Endpoints

The secondary endpoint is the percentage of subjects who maintain complete healing of EE over 6 months as assessed by endoscopy.

5.3 Additional Endpoints

Additional endpoints include:

- The percentage of days with neither daytime nor nighttime heartburn over the 8 weeks of the Healing Period as assessed by the daily diary.
- The percentage of days with neither daytime nor nighttime heartburn over the 6 months of the Maintenance Period as assessed by the daily diary among the subjects who were healed at Week 8.
- The percentage of days without rescue medication use over the 8 weeks of the Healing Period as assessed by the daily diary.
- The percentage of days without rescue medication use over the 6 months of the Maintenance Period as assessed by the daily diary among the subjects who were healed at Week 8.
- The severity of GERD symptoms at Weeks 4 and 8 as assessed by the investigator during the Healing Period.
- The severity of GERD symptoms at Months 1, 3, and 6 as assessed by the investigator during the Maintenance Period.

5.4 Safety Assessments

Safety will be assessed by AEs, clinical laboratory evaluations (including gastrin), vital signs, physical examination, and ECGs.

6.0 DETERMINATION OF SAMPLE SIZE

A total of 450 subjects with EE documented during Screening are planned to be enrolled into this study. Approximately 300 subjects are expected to enter the Maintenance treatment period.

Assuming a 10% dropout rate during the Healing Period and an 85% healing rate at Week 8 for both lansoprazole and dexlansoprazole, 225 subjects per arm will provide at least 80% power at the 1-sided 0.025 level of significance to meet the noninferiority criteria between lansoprazole and dexlansoprazole. Noninferiority to lansoprazole will be declared if the lower bound of the confidence interval for the difference in healing rates is greater than -10%.

The fixed noninferiority margin of -10% is based on a double-blind, parallel-group, comparative study that evaluated EE healing rates after an 8-week treatment period with lansoprazole 30 mg QD or placebo. In this study, the difference in response rate between the lansoprazole 30 mg dose group and the placebo group was 40.4%; the lower limit of the 2-sided 95% confidence interval was 25.9%. Hence, even with a conservative assumption of this lower bound as the treatment effect of lansoprazole 30 mg, a -10% noninferiority margin would assure that dexlansoprazole 30 mg retains more than 60% of the treatment effect of lansoprazole 30 mg.

Assuming a 33% dropout rate during the Maintenance Period and that maintenance rates are 14% and 66% for placebo and dexlansoprazole 30 mg, respectively, 150 subjects per arm will have at least 99% power at the 2-sided 0.05 level of significance to detect a difference between the treatment groups.

7.0 METHODS OF ANALYSIS AND PRESENTATION

7.1 General Considerations

Statistical analysis will be performed using the SAS System, Version 9.2 or higher.

All study-related raw data for enrolled subjects, including derived data, will be presented in data listings. Continuous data will be summarized using number of subjects, mean, standard deviation, median, minimum, and maximum. Categorical data will be summarized using the number and percentage of subjects for each category where appropriate.

7.1.1 Definition of Study Days and Visit Window

Study day will be calculated relative to the date of the first dose of study drug in the study. The study day prior to the first dose of study drug will be calculated as:

$$\text{Date of assessment/event} - \text{date of first dose of study drug.}$$

The study day on or after the first dose of study drug will be calculated as:

$$\text{Date of assessment/event} - \text{date of first dose of study drug} + 1.$$

Baseline is defined as the last non-missing measurement prior to or on Study Day 1 (prior to first dose). The baseline values for the Maintenance Period will be the assessment performed at the Week 8 visit of the Healing Period. The visit windows for each post baseline visit are defined in [Table 7.a](#). If a subject has more than 1 measurement in the same visit window, the measurement closest to the scheduled visit will be used. If 2 measurements in the same window are of equal distance to the scheduled visit, the measurement that occurs after the scheduled visit will be used. If 2 or more measurements occur on the same day, the last value obtained will be used.

Table 7.a Visit Windows for Healing Period

Visit	Scheduled Day	Safety Labs	Serum Gastrin	Vital Signs	ECG	Endoscopy	GERD Symptoms Investigator Assessment
Baseline	Day -1	≤1	≤1	≤1	≤1	≤1	≤1
Week 4	Day 28	2-42	NA	2-42	NA	NA	2-42
Week 8	Day 56	43-70	2-70	43-70	NA	2-70	43-70

Note: Safety labs (including gastrin), vital signs, and ECG data obtained more than 7 days after the last day of study drug and efficacy data obtained more than 7 days after the last day of study drug will not be included in the analyses.

Additionally, for subjects with healed EE by Week 8 who are randomized and receive at least 1 dose of maintenance study drug, the window selection for the Week 8 Visit will include only measurements assessed on or before the date of the first dose of maintenance period study drug; for visits during the Maintenance of Healed EE Period, the window selection will only include measurements assessed after the date of the first dose of maintenance period study drug.

The summary of visits during the maintenance period will be relative to the start of maintenance treatment rather than relative to the start of the study. The table below summarizes the visit windows for each visit during the Maintenance of Healed EE Period.

For the purpose of the diary compliance calculation and derivation of diary-based endpoints, the last day of study drug in each period will not be included since the subject will not be expected to have completed the diary entries for that day by the Week 8 or month 6 Final Visit. Therefore, summaries for the healing period weeks of treatment will include Study Day 1 through Study Day 70 or the day before the last dose of healing period study drug, or the day before the first dose of maintenance study drug, whichever occurs first; summaries for the Maintenance period will include the day of the first dose of maintenance study drug through maintenance Study Day 180 or the day before the last dose of maintenance study drug, whichever occurs first.

Table 7.b Visit Windows for Maintenance Period

Visit	Scheduled Day	Safety Labs and Vital Signs	Serum Gastrin	ECG	Endoscopy	GERD Symptoms Investigator Assessment
Maintenance Baseline	-1M	≤1M	≤1M	≤1M	≤1M	≤1M
Month 1	30M	2M-60M	2M-60M	NA	2M-60M	2M-60M
Month 3	90M	61M-135M	61M-135M	NA	61M-135M	61M-135M
Month 6	180M	136M-210M	136M-210M	2M-210M	136M-210M	136M-210M

Note: Safety laboratory (including gastrin), vital signs, and ECG data obtained more than 7 days after the last day of study drug of Maintenance period and efficacy data obtained more than 7 days after the last day of study drug of Maintenance period will not be included in the analyses.
 M=Maintenance Period.

7.2 Analysis Sets

The full analysis set (FAS) will be defined separately for the Healing and Maintenance Periods. The full analysis set for the Healing Period (FAS – H) will include all randomized subjects who have documented EE at screening and receive at least 1 dose of study drug during the first 8 weeks of treatment. The full analysis set for the Maintenance Period (FAS – M) will include all subjects with healed EE by week 8 who are randomized and receive at least 1 dose of study drug during 6 months of maintenance treatment.

The safety analysis set will be defined separately for the healing period and for the Maintenance Period. The safety analysis set for the Healing Period (Safety Set – H) will include all subjects who receive at least 1 dose of study drug during Healing Period. The safety analysis set for the Maintenance Period (Safety Set – M) will include all subjects with healed EE by Week 8 who are randomized and receive at least 1 dose of study drug during 6 months of maintenance treatment.

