9.1.16 Endoscopy

Endoscopy should be performed while subjects are fasted and according to the usual practice of the institution (ie, with regard to premedications or concomitant therapies, as long as they are not prohibited in Section 7.3 of this protocol).

The investigator (or designee) will record the results of endoscopy (including results of the LA classification and other gradings) performed promptly in the subject's medical record.

To ensure the accuracy of the EE evaluation according to LA grading, a 2nd review process of the endoscopic images will be established at each site. The 1st reviewer, ie, the endoscopist should take sufficient images or videotape the process at each endoscopic examination. The 2nd reviewer will evaluate the EE LA grading according to the endoscopic images.

- Preferably, the principal investigator performs as the 2nd reviewer and conducts the 2nd review in a timely manner after the endoscopy is performed by the 1st reviewer who is a subinvestigator in this study.
- In cases where the principal investigator is the 1st reviewer, a subinvestigator at the same site can be delegated as the 2nd reviewer and conducts the 2nd review in a timely manner.
- Only investigators (either principal investigators or subinvestigators) can be delegated as the 2nd reviewer.

If the LA grading by the 2 reviewers are consistent, this result becomes the final report. If not, the 2 reviewers will discuss their findings and reach a consensus which will then become the final report.

During Screening and at Week 8/Final Visit of the Healing Period, an endoscopy will be performed on all subjects to document the presence/absence of EE. Erosive esophagitis will be graded according to the LA Classification of Esophagitis Grading System ([Appendix E](#)).

The screening endoscopy must be performed within 14 days prior to randomization. Any reliable, documented results available from an endoscopy performed in a routine clinical setting (before signing of informed consent) within 14 days prior to randomization in the same institution will be accepted instead, given the invasive nature of the procedure.

Any Barrett's esophagus seen during screening endoscopy will exclude the subject from study. These endoscopic assessments will be recorded on the eCRF and a copy of the results should be kept with the subject's notes.

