7.11 Safety Analysis

All safety analyses will be performed using the Safety Analysis Set-H for the Healing Period, and using the Safety Analysis Set-M for the maintenance period. Results will be summarized by treatment group.

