7.11.1 Adverse Events

All AEs will be coded using the Medical Dictionary for Regulatory Activities (MedDRA).

A Treatment Emergent Adverse Event (TEAE) will be defined as an AE that starts or worsens on or after Study Day 1, and no more than 30 days after the last dose of study drug. All TEAEs will be listed by subject number and MedDRA coding. A listing of all unique coded terms will also be provided.

The following summaries of TEAEs will be presented separately:

- TEAEs for subjects who enter into the Healing Period, occurring during the 8 week healing period (ie, TEAE starts or worsens on or after the first dose of healing phase study drug and no more than 30 days after the last dose if a subject does not receive any maintenance study drug or before the first dose of maintenance study drug) will be summarized by treatment group using the Safety Analysis Set-H.
- TEAEs for subjects who enter into Maintenance period, occurring during the 6 months maintenance treatment period (ie, TEAE starts or worsens on or after the first dose of maintenance study drug and before 30 days after last dose of maintenance) will be summarized by treatment group using the Safety Analysis Set-M.

The number and percentage of subjects with TEAEs will be summarized in several different tables:

- All AEs by system organ class (SOC), high level term (HLT), and preferred term (PT).
- Treatment-related AEs (TRAEs) by SOC, HLT, and PT.
- Most frequent AEs by SOC and PT (sorted by frequency of PT occurring in $\geq 5\%$ of subjects).
- Most frequent TRAEs by SOC and PT (sorted by frequency of PT occurring in $\geq 2\%$ of subjects).
- Severity of all AEs by SOC and PT (mild, moderate, or severe).
- Severity of TRAEs by SOC and PT (mild, moderate, or severe).
- Relationship to study drug for all AEs by SOC and PT (not related, related).

A subject with 2 or more AEs within the same level of the MedDRA term will be counted only once in that level using the most extreme incident (most severe for the severity tables and related for the relationship to study drug tables).

Additionally, treatment-emergent serious AEs, deaths and TEAEs resulting in premature discontinuation from study drug will be listed and summarized by SOC and PT. The most frequent treatment-emergent non-serious AEs will also be summarized by SOC and PT.

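### Safety Set-M requires healed EE as well as dosing, so a subject dosed in Maintenance but finally graded not healed has post-dose safety data in neither period's summary tables

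*SAP*

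**What the plan says.** SAP 7.2 and protocol 13.1.1 define the sets in matching text.

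- FAS-M "will include all subjects with healed EE by week 8 who are randomized and receive at least 1 dose of study drug". Safety Set-M has the same wording apart from a capital letter, so membership needs three things: healed EE by Week 8, randomization and dosing.
- Safety Set-H "will include all subjects who receive at least 1 dose of study drug during Healing Period". It carries no condition on disease status.

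SAP 7.11 runs Maintenance safety analyses "using the Safety Analysis Set-M for the maintenance period". SAP 7.11.1 then sets two windows for treatment-emergent adverse events (TEAEs):

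- The Healing window extends to 30 days after the last dose "if a subject does not receive any maintenance study drug or before the first dose of maintenance study drug". For anyone who takes maintenance drug, it therefore ends at the first maintenance dose.
- The Maintenance window covers an event that "starts or worsens on or after the first dose of maintenance study drug and before 30 days after last dose of maintenance". These events "will be summarized by treatment group using the Safety Analysis Set-M".

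On who counts as healed, protocol 9.1.16 has two site reviewers grade each endoscopy, and their agreed or consensus grade is the final report. Preferably the principal investigator is the second reviewer and "conducts the 2nd review in a timely manner after the endoscopy is performed" by a subinvestigator. No deadline relative to Maintenance randomization is given.

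**The concern.** A safety set normally holds everyone exposed. Safety Set-M is FAS-M under another name: an efficacy finding decides whether an exposed subject's safety data are tabulated. Neither document explains why Maintenance differs from Healing in this respect.

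The condition does nothing while everyone dosed in Maintenance is healed. It takes effect when someone is dosed and the final grade is not healed, either because the consensus came after dosing or because of a randomization error. That subject has been exposed to dexlansoprazole 30 mg or placebo, yet post-dose events drop out of both the numerator and the denominator of the Maintenance tables. Whether to include the subject would then be an unplanned decision.

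**Working it through.** The plan gives no figure on this point, so the check is a logical one: apply the set definitions (SAP 7.2) and the TEAE windows (SAP 7.11.1) to every combination of healed status, maintenance dosing and event timing. All subjects here were dosed in Healing and so belong to Safety Set-H.

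| Healed (final grade) | Maintenance dose taken | Event timing | Healing table | Maintenance table as written | Maintenance table, dosing-only set |
|---|---|---|---|---|---|
| yes | yes | before first maintenance dose | yes | no | no |
| yes | yes | on or after first maintenance dose | no | yes | yes |
| yes | no | during Healing treatment | yes | no | no |
| yes | no | within 30 days after last Healing dose | yes | no | no |
| no | yes | before first maintenance dose | yes | no | no |
| no | yes | on or after first maintenance dose | **no** | **no** | yes |
| no | no | during Healing treatment | yes | no | no |
| no | no | within 30 days after last Healing dose | yes | no | no |

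As written, 6 combinations fall in the Healing table and 1 in the Maintenance table: 6 + 1 = 7 of 8. The sixth row is in neither. With a dosing-only set, 6 + 2 = 8 of 8, each counted once.

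**Can the sixth row occur?** Several protocol provisions bear on timing:

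- Section 9.3.4 treats the Week 8 visit as Maintenance Day -1, and 9.3.4.1 places randomization and dispensing there.
- Section 8.1.3 has the last Healing dose taken on the morning of that visit.
- Appendix A, footnote (m), puts the first maintenance dose about 24 hours after the last Healing dose. It makes randomization depend on endoscopy confirming healing, without naming the second review.
- Section 9.1.16 asks only that the second review be timely.

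On that schedule, the image review, any disagreement and the consensus have about a day before first dosing, and no rule makes them finish first. Protocol 7.5 also foresees entry failures discovered after randomization. Neither document says how a subject dosed and later graded not healed is to be analysed.

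**What else is affected?** SAP 7.11.2 (laboratory) and 7.11.3 (vital signs) use Safety Set-M for Maintenance, so those summaries share the gap. The Month 6 ECG cross-tabulation does not, because SAP 7.11.4 assigns it to Safety Set-H.

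**Visit windows.** SAP 7.1.1 separates Week 8 from Maintenance measurements at the first maintenance dose, but only for healed, randomized, dosed subjects. The subject in the sixth row has no rule for that split.

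**The case against.** The strongest reply is that the condition is merely descriptive. The protocol admits only healed subjects to Maintenance (6.1, 8.1, 8.3, 9.1.15, 9.1.16, 9.3.4). If every subject is handled that way, Safety Set-M equals everyone dosed. The natural reading is that the final report decides entry, and no section says that a subject may be randomized on the first reader's grade alone. The safety-set definition does not name the consensus reading either. It could mean healed as judged when the subject was randomized, which would keep a re-graded subject in.

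Much of this stands. The gap is contingent, and its mechanism rests on what the documents leave open. They do not require the second review to precede dosing, and they do not say which reading defines membership. If the condition is redundant, removing it changes nothing; if it operates, it excludes exposed subjects.

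A reader might infer three stronger things, none of which the documents support:

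- **That the events are lost.** SAP 7.11.1 lists all TEAEs, and SAP 7.1 lists all raw data for enrolled subjects. The loss is from summary counts and denominators.
- **That all of the subject's events go uncounted.** Those before the first maintenance dose remain in the Healing table.
- **That several subjects must be affected.** Assuming that 1% to 3% of about 300 entrants are re-graded or mis-randomized gives 300 × 0.01 = 3 to 300 × 0.03 = 9. That rate is pure assumption. Most grading disagreement (A against B, say) is irrelevant: only a change from healed to not healed after dosing, or an outright randomization error, counts.

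The blinded data review (protocol 13.1) and the summary of significant deviations (SAP 7.3) could bring such a subject to light, but they do not alter the set definition.

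**Conclusion.** The point holds as a minor defect in a set definition. For a subject who receives maintenance drug and is finally graded not healed, or is randomized in error, TEAEs on or after the first maintenance dose and Maintenance laboratory and vital-sign data fall outside the period summaries.

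The number of subjects is unknown and may be zero. The conclusion assumes that healed status in the definition means the final consensus grade, and that dosing can precede that grade or follow a randomization error; the documents exclude neither. Membership turns on the Week 8 endoscopy, which predates maintenance treatment, so if grading stays blind the main effect is incomplete tables, not a systematic imbalance between arms. No primary or secondary efficacy conclusion changes.

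**What to change.** 1. In SAP 7.2 and protocol 13.1.1, define Safety Set-M as all subjects who receive at least one dose of Maintenance study drug. Keep the healed-EE condition for FAS-M only.
2. In SAP 7.1.1, make the same change to the rule that separates Week 8 from Maintenance measurements, so that it applies to anyone who takes a maintenance dose. Changing the set definition alone would bring a non-healed subject into the set without a rule for that split.
3. Add a listing of subjects in Safety Set-M but not in FAS-M, so that any difference between the sets is visible.

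The cost is small wording edits in three places and one extra listing. No efficacy analysis is touched. The change is best made before unblinding, so that membership is settled without knowledge of treatment.
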